## 5.2. Exclusion Criteria

Participants are excluded from the study if any of the following criteria apply (unless stated otherwise, criteria apply to both FC and IBS-C participants):

1.	Medical Conditions
1.01	For FC participants only: Participant meets Rome III criteria for Child/Adolescent IBS: At least once per week for at least 2 months before the Screening Visit, the participant has experienced abdominal discomfort (an uncomfortable sensation not described as pain) or pain associated with 2 or more of the following at least 25% of the time: 
 
• Improvement with defecation
 
• Onset associated with a change in frequency of stool
 
• Onset associated with a change in form (appearance) of stool
 

1.02	Participant reports having more than 1 loose, mushy stool (eDiary-recorded stool consistency of 6 on the Pediatric Bristol Stool Form Scale [p-BSFS]) or any watery stool (eDiary-recorded stool consistency of 7 on the p-BSFS) with any SBM that occurred in the absence of laxative use on the calendar day of the BM or the calendar day before the BM during the 14 days before the randomization day and up to the randomization (including the morning eDiary assessments reported before

	administration of first dose of double-blind study intervention on the randomization day)
1.03	Participant has a history of non-retentive fecal incontinence
1.04	Participant has (a) fecal impaction at Visit 2 after failing outpatient clean-out during the Screening Period or (b) fecal impaction at Visit 3
1.05	Participant has required manual disimpaction any time prior to randomization
1.06	Participant currently has both unexplained and clinically significant alarm symptoms (lower GI bleeding [rectal bleeding or heme-positive stool], iron-deficiency anemia, or any unexplained anemia, or weight loss) and systemic signs of infection or colitis, or any neoplastic process
1.07	Participant has clinically significant findings on a physical examination, vital sign assessment, ECG, or clinical laboratory test as determined by the investigator based on consideration of whether the finding could represent a safety concern or a condition that would be exclusionary, could prevent the participant from performing any protocol assessments, or could confound study assessments.
1.08	Participant has a history of drug or alcohol abuse.

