#### 5.4. Screen Failures

Screen failures are defined as participants who consent to participate in the clinical study but are not subsequently entered in the study. A minimal set of screen failure information is required to ensure transparent reporting of screen failure participants to meet the Consolidated Standards of Reporting Trials (CONSORT) publishing requirements and to respond to queries from regulatory authorities. Minimal information includes demography, screen failure details, eligibility criteria, and any SAE.

Individuals who do not meet the criteria for participation in this study (screen failures) may be rescreened. A participant who has not yet received any e-Diary training at Visit 2 (Preintervention) may be rescreened under special circumstances (eg, failure to meet prohibited medication washout requirements). All requests for rescreening must be sent to the sponsor and approved by the study physician. Any participant approved for rescreening by the study physician will be assigned a new participant identification (PID) and repeat the study screening procedures.

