#### 8.3.1. Adverse Events of Special Interest (AESIs)

AESIs are defined as significant volume depletion and/or significant electrolyte abnormalities and/or ECG abnormalities that are considered by the investigator or sponsor to be related to diarrhea. The investigator should contact the sponsor if there is any question whether the criterion for an AESIs has been met. All AESIs must be reported to the sponsor as described in Section 10.3.

**8.3.2. Time Period and Frequency for Collecting Adverse Events, Serious Adverse Events, and Adverse Events of Special Interest Information**

- At each visit, participants are to be queried regarding any AEs or SAEs that have occurred since the previous visit. Participants will be asked to volunteer information with a nonleading question such as, “How do you feel since your last visit?” Study site personnel will record all pertinent information in the participant’s eCRF. All SAEs from the signing of the ICF until 30 days after the last dose of study intervention will be collected at the timepoints specified in the SoA (Section 1.3), and as observed or reported spontaneously by study participants.
- All AEs from the signing of the ICF until 30 days after the last dose of study intervention will be collected at the timepoints specified in the SoA (Section 1.3), and as observed or reported spontaneously by study participants.
- Medical occurrences that begin before the start of study intervention, but after obtaining informed consent, will be recorded in the AE section of the eCRF.

All SAEs and serious AESIs will be recorded and reported to the sponsor or designee within 24 hours on an SAE form, as indicated in Section 10.3. Non-serious AESIs do not require submission on an SAE form; rather, these events only need to be entered into the eCRF. The investigator will submit any updated SAE data to the sponsor within 24 hours of it being available.

Investigators are not obligated to actively seek AE or SAE information after conclusion of the study participation. However, if the investigator learns of any SAE including a death, at any time after a participant has been discharged from the study, and he/she considers the event to be reasonably related to the study intervention or study participation, the investigator must promptly notify the sponsor.

The method of recording, evaluating, and assessing causality of AEs and SAEs and the procedures for completing and transmitting SAE reports are provided in Section 10.3.

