11.1 Adverse Events

Adverse events will be coded by system organ class and preferred term using the *Medical Dictionary for Regulatory Activities*, version 23.0 or newer.

An AE will be considered a treatment-emergent adverse event (TEAE) if

- The AE began on or after the date of the first dose of study intervention; or
- The AE was present before the date of the first dose of study intervention, but increased in severity or became serious on or after the date of the first dose of study intervention

An AE that occurs more than 30 days after the last dose of study intervention will not be counted as a TEAE.

An AE will be considered a treatment-emergent serious adverse event (TESAE) if it is a TEAE that additionally meets any SAE criterion.

The number and percentage of participants reporting TEAEs in each study intervention group will be tabulated by descending percentage in any group, by system organ class and preferred term, and further categorized by severity and causal relationship to the study intervention. If more than 1 AE is coded to the same preferred term for the same participant, the participant will be counted only once for that preferred term using the greatest severity and strictest causality for the summarization by severity and causal relationship. The above summaries of TEAEs, further categorized by severity and causal relationship will also be provided within each age group. If there are 5 or less participants with severe or related TEAEs in any study intervention group, the

corresponding age group summaries for TEAEs by severity or causal relationship will not be provided.

The incidence of common ($\geq 5\%$ of participants in any study intervention group) TEAEs will be summarized by system organ class, preferred term, and study intervention group.

Summary tables will be provided for participants with TESAEs, AEs of special interest, and participants with AEs leading to discontinuation.

For all screened participants, separate listings will be presented for participants who died, participants with SAEs, participants with AEs leading to premature discontinuation, and participants with AEs of special interest (AESI). AEs during the Postintervention Period will also be included in the listings. A listing of all AEs will also be presented.

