6.4 SAFETY POPULATION

The Safety Population will consist of all participants in the Randomized Population who receive at least 1 dose of double-blind study intervention.

Participants will be summarized according to the study intervention they actually received for all safety analysis variables/endpoints. If a participant received study intervention other than randomized study intervention, actual study intervention received will be determined based on the study intervention received for the majority of the double-blind Study Intervention Period. If there is a tie, the higher dose will be considered the actual study intervention for that participant. The actual study intervention will be listed for the participants in the listing related to study intervention dosing information.

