11.0 SAFETY ANALYSES

The safety analysis will be performed using the Safety Population. The safety parameters will include adverse events (AEs) and clinical laboratory parameters, vital sign (including postural), electrocardiographic (ECG) parameters, height, and weight. For each safety parameter of the clinical laboratory, vital signs, height, weight, and ECG parameters, the last non-missing safety assessment before the first dose of study intervention will be used as the baseline for all analyses of that safety parameter. Continuous variables will be summarized by number of participants and mean, SD, median, minimum, and maximum values. Categorical variables will be summarized by number and percentage of participants. The safety summaries will be provided by study intervention group.

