11.1 ADVERSE EVENTS

Adverse events will be coded by system organ class and preferred term using the *Medical Dictionary for Regulatory Activities*, version 23.0 or newer.

An AE will be considered a treatment-emergent adverse event (TEAE) if

- The AE began on or after the date of the first dose of study intervention; or
- The AE was present before the date of the first dose of study intervention, but increased in severity or became serious on or after the date of the first dose of study intervention

An AE that occurs more than 30 days after the last dose of study intervention will not be counted as a TEAE.

An AE will be considered a treatment-emergent serious adverse event (TESAE) if it is a TEAE that additionally meets any SAE criterion.

The number and percentage of participants reporting TEAEs in each study intervention group will be tabulated by descending percentage in any group, by system organ class and preferred term, and further categorized by severity and causal relationship to the study intervention. If more than 1 AE is coded to the same preferred term for the same participant, the participant will be counted only once for that preferred term using the greatest severity and strictest causality for the summarization by severity and causal relationship. The above summaries of TEAEs, further categorized by severity and causal relationship will also be provided within each age group. If there are 5 or less participants with severe or related TEAEs in any study intervention group, the corresponding age group summaries for TEAEs by severity or causal relationship will not be provided.

The incidence of common ($\geq 5\%$ of participants in any study intervention group) TEAEs will be summarized by system organ class, preferred term, and study intervention group.

Summary tables will be provided for participants with TESAEs, AEs of special interest, and participants with TEAEs leading to premature discontinuation of study intervention.

For the Safety Population, separate listings will be presented for participants who died, participants with SAEs, participants with AEs leading to premature discontinuation, and participants with AEs of special interest. AEs during the Postintervention Period will also be included in the listings. Listing of all AEs will also be presented.

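### The FC SAP lists deaths, SAEs, AEs leading to discontinuation and AESIs for dosed children only, so run-in deaths and SAEs in children screened but never dosed are left out of those listings

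*SAP*

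**What the plan says.** **FC SAP, Section 11.1.** The listings of deaths, SAEs, AEs leading to premature discontinuation and AESIs are tied to one population: "For the Safety Population, separate listings will be presented for participants who died, participants with SAEs". The paragraph ends with "Listing of all AEs will also be presented", which names no population.

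**FC SAP, Sections 11.0 and 6.4.** The general rule is "The safety analysis will be performed using the Safety Population", and the definition is "The Safety Population will consist of all participants in the Randomized Population who receive at least 1 dose of double-blind study intervention".

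**IBS-C SAP, Section 11.1.** The matching sentence reads "For all screened participants, separate listings will be presented for participants who died, participants with SAEs".

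**Protocol, Section 8.3.2.** Collection starts before the run-in: "All SAEs from the signing of the ICF until 30 days after the last dose of study intervention will be collected". The same window applies to all AEs.

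**Protocol, Section 5.4.** For screen failures, "Minimal information includes demography, screen failure details, eligibility criteria, and any SAE".

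**Protocol, Section 5.2.** Criterion 1.04 excludes children with "a) fecal impaction at Visit 2 after failing outpatient clean-out during the Screening Period or (b) fecal impaction at Visit 3". Criterion 1.05 excludes any child who has needed manual disimpaction before randomization.

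**FC SAP, Section 7.0.** For children who are screened and not randomized, the plan is a tabulation of failures and their recorded reasons.

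**The concern.** The run-in contains trial procedures. Prohibited laxatives are stopped before the Preintervention Period in favor of permitted rescue medication, and a child found impacted at Visit 1 receives a disimpaction regimen (Protocol, Sections 6.5.1, 6.5.2 and 8.2.1). The AESI definition, which concerns volume depletion, electrolyte or ECG abnormalities related to diarrhea, does not require exposure to study drug, so a run-in event could meet it.

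A serious event in this period is recorded. Whether it reaches the FC listings depends on whether the child is later randomized and dosed. That filter is not neutral, since some run-in outcomes themselves bar a child from randomization. The two parts of one trial would also report run-in deaths and SAEs on different bases. Protocol Section 9.2.5.2 says the IBS-C safety analyses follow the FC methods except that summaries are given by dose group. Sections 17.0 and 18.0 of the FC SAP give no reason for a narrower population.

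At stake is whether the FC report accounts for every death and SAE collected after consent.

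**Working it through.** No power or sample-size formula applies. The check sets the rules side by side and follows each group of children through them.

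**1. Length of the run-in.** The Schedule of Activities gives Screening 14 to 28 days and Preintervention 14 to 21 days.

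- Shortest: 14 + 14 = 28 days = 4 weeks
- Longest: 28 + 21 = 49 days = 7 weeks
- Adding 12 weeks of intervention and 1 week after it: 4 + 12 + 1 = 17 weeks and 7 + 12 + 1 = 20 weeks

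This reproduces the 17 to 20 weeks in the synopsis, so the run-in length is right.

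**2. Who is in the named FC listings.**

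| FC children | SAEs collected from consent | In the named Section 11.1 listings |
|---|---|---|
| Randomized and dosed | Yes | Yes; the SAE listing is not limited to treatment-emergent events, so run-in SAEs are included |
| Impacted at Visit 1, clear at Visit 2, later dosed | Yes | Yes |
| Impacted at Visit 2 after clean-out, impacted at Visit 3, or manual disimpaction before randomization | Yes | No |
| Not randomized for any other reason | Yes | No |
| Randomized, never dosed | Yes | No |

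Under the IBS-C rule, all five rows would be in the listings.

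**3. What else could show the events.** The Section 7.0 failure table covers all screened participants, but it gives counts and reasons without event detail. The all-AE listing might cover them. Its sentence names no population, and Section 11.0 points to the Safety Population.

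**4. Illustration of how many children are outside the listings.** The documents give no FC screen-failure rate. Let f be the assumed share of screened children who are never randomized. To reach the 326 target, the number screened is 326 / (1 − f), rounded up.

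- f = 20%: 326 / 0.8 = 407.5, so 408 screened and 408 − 326 = 82 outside
- f = 40%: 326 / 0.6 = 543.3, so 544 screened and 544 − 326 = 218 outside
- f = 60%: 326 / 0.4 = 815 screened and 815 − 326 = 489 outside

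Any child randomized and never dosed adds to these. The figures count children, not events.

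**The case against.** The strongest reply is that little is lost. SAEs from consent onward go to the sponsor within 24 hours, and a DSMB oversees safety. The FC objective is linaclotide against placebo, and an uncontrolled listing of screen failures bears on neither that comparison nor the TEAE tables. The listing specifications are in a separate document, which might define the all-AE listing more widely. All of this stands. It limits the point to what the study report shows, but it does not alter the population stated in Section 11.1.

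Several stronger readings are tempting and are not supported:

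- **That every impacted child is kept from dosing.** A child impacted at Visit 1 and clear at Visit 2 may continue. If dosed, that child's run-in SAEs are listed.
- **That the omission of impaction is total.** Exclusion for impaction can appear as a failure reason for all screened participants. Impaction is also not an SAE in itself: Appendix 3 does not count expected signs of the disease as AEs unless they are more severe than expected.
- **That the events appear in no FC output.** The all-AE listing has no stated population, so this is an inference from Section 11.0.
- **That the two SAPs cover the same sites.** Only North American sites randomize IBS-C participants, while FC also recruits in Europe and the Middle East. The comparison rests on the shared protocol and run-in schedule.
- **That the run-in's share of a completer's time measures the loss.** Completers were dosed, and their run-in SAEs are listed.
- **That a wider listing would measure the risk of stopping laxatives.** It has no control group, permitted rescue replaces the stopped laxatives, and stable fiber, bulk laxatives and stool softeners may continue.

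**Conclusion.** The point holds as a reporting gap that should be closed. Under Section 11.1 of the FC SAP, deaths, SAEs and AESIs in children screened but never dosed fall outside the listings made for them. The data are collected, and the IBS-C SAP already uses the wider population. The gap is firm for the named listings. For the all-AE listing it is probable and rests on reading Section 11.0 as the default.

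The size in events is unknown. Under assumed non-randomization shares of 20% to 60%, about 82 to 489 children would be outside the listings. Turning that into a count of SAEs would need an SAE rate that the documents do not give. The conclusion does not depend on the illustration: a single such death or SAE would be left out under the rule as written. Efficacy results, TEAE tables, alpha, power and sample size are not affected.

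**What to change.** In FC SAP Section 11.1:

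1. Change the population of the death, SAE, discontinuation and AESI listings from the Safety Population to all screened participants, as in IBS-C SAP Section 11.1.
2. State the same population for the all-AE listing.
3. Flag each event by study period (screening, preintervention, intervention, postintervention) and by whether the child was randomized and dosed.
4. Report deaths and SAEs in non-dosed children separately, so that they are not mixed with the treatment groups.

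Add a clause to Section 11.0 exempting these listings from the Safety Population rule, and align the separate listing specifications.

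The cost is a short SAP edit and a wider listing filter. SAEs are already collected for screen failures. For non-serious AEs, Section 8.3.2 requires collection from consent while the minimal data set in Section 5.4 names only SAEs, so it is worth confirming what the database holds for these children. Children who were never randomized have no treatment assignment, so listing their events discloses nothing about the comparison.

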11.2 CLINICAL LABORATORY PARAMETERS

Descriptive statistics for clinical laboratory values (in International System of Units [SI] units) and changes from the baseline values at each assessment time point will be presented by study intervention group for the following laboratory parameters:

- Hematology: Absolute and differential white blood cell count, erythrocyte count, hemoglobin, hematocrit, platelet count, red blood cell count, and red blood cell indices (mean corpuscular volume, mean corpuscular hemoglobin, and mean corpuscular hemoglobin concentration)
- Chemistry: Sodium, potassium, calcium, chloride, bicarbonate, magnesium, phosphate, glucose, blood urea nitrogen, creatinine, total protein, alkaline phosphatase (ALP), albumin, total bilirubin (TBL), alanine aminotransferase (ALT), aspartate aminotransferase (AST), total cholesterol
- Urinalysis: Specific gravity and pH

Clinical laboratory test values will be considered potentially clinically significant (PCS) if they meet either the lower-limit or higher-limit PCS criteria listed in [Table 11-1](#). The number and percentage of participants who have PCS postbaseline clinical laboratory values will be tabulated by study intervention for the double-blind Intervention Period. The percentages will be calculated relative to the number of participants with available non-PCS baseline values and at least 1 postbaseline assessment for the double-blind Intervention Period. The numerator will be the total number of participants with available non-PCS baseline values and at least 1 PCS postbaseline value for the double-blind Intervention Period. A supportive tabular display of participants with PCS postbaseline values will be provided, including the PID number, baseline and all postbaseline (including non-PCS) values. In this listing, any participant with PCS value (if any) during the Post-intervention period will also be included.

In addition, a tabular display showing all AEs that occurred in participants who had PCS postbaseline clinical laboratory values will be provided.

Shift tables from baseline to the end of double-blind Intervention Period for clinical laboratory parameters listed above will be presented by study intervention group for the following categories: low, normal, and high, which are provided by lab vendor.

Table 11-1 Criteria for Potentially Clinically Significant Laboratory Results

Parameter	SI Unit	Lower Limit	Higher Limit
CHEMISTRY			
Albumin	g/L	$< 0.9 \times \text{LLN}$	$> 1.1 \times \text{ULN}$
Alanine aminotransferase (ALT)	U/L	—	$\geq 3 \times \text{ULN}$
Alkaline phosphatase	U/L	—	$\geq 1.2 \times \text{ULN}$: 6-12 (inclusive), male & female; 13-15 (inclusive), male $\geq 3 \times \text{ULN}$: 13-15 (inclusive), female; 16- 17 (inclusive), male & female
Aspartate aminotransferase (AST)	U/L	—	$\geq 3 \times \text{ULN}$
Bicarbonate	mmol/L	$< 0.9 \times \text{LLN}$	$> 1.1 \times \text{ULN}$
Bilirubin, total	$\mu\text{mol/L}$	—	$> 1.5 \times \text{ULN}$
Calcium	mmol/L	$< 0.9 \times \text{LLN}$	$> 1.1 \times \text{ULN}$
Chloride	mmol/L	$< 0.9 \times \text{LLN}$	$> 1.1 \times \text{ULN}$
Cholesterol, Total	mmol/L	—	$> 1.6 \times \text{ULN}$
Creatinine	$\mu\text{mol/L}$	—	$> 1.3 \times \text{ULN}$
Glucose, random, serum	mmol/L	$< 0.8 \times \text{LLN}$	$> 1.4 \times \text{ULN}$
Potassium	mmol/L	$< 0.9 \times \text{LLN}$	$> 1.1 \times \text{ULN}$
Protein, total	g/L	$< 0.9 \times \text{LLN}$	$> 1.1 \times \text{ULN}$
Sodium	mmol/L	$< 0.9 \times \text{LLN}$	$> 1.1 \times \text{ULN}$
Urea Nitrogen (BUN)	mmol/L	—	$> 1.2 \times \text{ULN}$
HEMATOLOGY			
Basophils, absolute cell count	$10^9/\text{L}$	—	$> 3 \times \text{ULN}$
Eosinophils absolute cell count	$10^9/\text{L}$	—	$> 3 \times \text{ULN}$
Lymphocytes absolute cell count	$10^9/\text{L}$	$< 0.7 \times \text{LLN}$	$> 1.3 \times \text{ULN}$
Monocytes, absolute cell count	$10^9/\text{L}$	$< 0.5 \times \text{LLN}$	$> 2.0 \times \text{ULN}$
Neutrophils, absolute cell count	$10^9/\text{L}$	$< 0.8 \times \text{LLN}$	$> 1.5 \times \text{ULN}$
Hematocrit	Ratio	$< 0.9 \times \text{LLN}$	$> 1.1 \times \text{ULN}$
Hemoglobin	g/L	$< 0.9 \times \text{LLN}$	$> 1.1 \times \text{ULN}$
Platelet count	$10^9/\text{L}$	$< 0.5 \times \text{LLN}$	$> 1.5 \times \text{ULN}$
Red blood cell count	$10^{12}/\text{L}$	$< 0.9 \times \text{LLN}$	$> 1.1 \times \text{ULN}$
White blood cell count	$10^9/\text{L}$	$< 0.7 \times \text{LLN}$	$> 1.5 \times \text{ULN}$
URINALYSIS			
pH	—	$< 0.9 \times \text{LLN}$	$> 1.1 \times \text{ULN}$
Specific gravity	—	—	$> 1.1 \times \text{ULN}$

LLN = lower limit of normal value provided by the laboratory; SI = *Le Système International d'Unités* (International System of Units); ULN = upper limit of normal value provided by the laboratory.

